8.3 Trial randomisation

After all applicable screening assessments have been performed, subjects who have met all inclusion criteria and none of the exclusion criteria will be randomized (1:1) to one of the following groups and will receive a unique randomization number:

- 1) No screening (intervention)
- 2) 3x3 screening (comparator)

The randomization list will be prepared using SAS 9.4 (SAS Institute, Cary NC). The randomization of the participants will be done within RedCap, a GCP-compliant electronic data capture software tool that the CTU has used to good effect in previous studies for this purpose. To ensure (approximate) treatment balance within study sites, the randomization list will be blocked by site using variable block sizes. The overview of the randomization list will not be shared with the investigators until the trial database is locked.

8.4 Blinding

This study will be unblinded.

Study Participants: The participant will not be explicitly informed to which intervention arm they have been randomized. However it will not be possible to completely blind the participants to which arm they are in, since those in the screening arm who test positive will be recalled for treatment of an asymptomatic infection. In addition, participants will be able to see which arm they are in the 3 weeks after enrolment if they login online to obtain their Ng/Ct results (a service that is in the process of becoming available to all PrEP recipients). If they are in the screening arm they will be able to see either a positive or a negative result for Ng/Ct. If they are in the no-screening arm, no test result will be visible. From this they will be able to deduce which arm they are in.

Doctors and study nurses: The attending doctors will not be blinded. Blinding the attending doctors would be very difficult within this study design as a week after each study visit, the doctors will receive the results of the Ng/Ct screening tests, but only for the participants in the 3x3 screening arm. At this point the doctor will be able to deduce which arm the participant is in. As a result, we have decided that the attending doctors will not be blinded to study arm allocation.

Statistician: The study statistician will be blinded until the statistical analysis plan (SAP) is approved.

8.5 Unblinding

Unblinding will not be necessary. If a participant urgently requires knowing if they are infected with Ng/Ct or not this will be done by repeat testing for these infections. If this occurs, this participant will not be excluded from the study.

8.6 Baseline data

The following baseline data will be collected during the screening/enrolment visit:

- Demographics: year of birth, gender,
- Sexual behaviour: number of sex partners in preceding 3 months, number of sex partners with condomless anal sex
- STI history: all STIs (Ct, Ng, syphilis, hepatitis C) diagnosed in the last 12 months before screening
- Antibiotics usage: all antibiotics used in the last 6 months before screening

8.7 Trial assessments

These assessments will be performed according to standard of care at each participating centre. In certain centres such as HSP the laboratory tests are performed the week before the clinic visit. These laboratory assessments will be considered to be the laboratory results for that particular visit. Participants in the non-screening arm will not be informed of their results at month 3, 6 and 9. They will only be informed about the result of the sample taken at month 0 and month 12.

Screening/enrolment visit (Day 0):

- Eligibility check
- Informed Consent Procedure
- Demographic and question regarding sexual behaviour
- PrEP questionnaire (only at ITM)
- Ask if symptoms compatible with STI
- Physical examination if symptomatic
- STI history last 12 months
- Antibiotic usage last 6 months
- Randomization
- Collection of results of syphilis and HIV testing (performed according to routine practice)
- Sample collection (according to standard practice of the participating sites.):
 - o Urine sample (first-void) (Ng/Ct NAAT)
 - o Pharyngeal swab (Ng/Ct NAAT)
 - o Anorectal swab (Ng/Ct NAAT)

Visit month 3 (can be between one week earlier and 6 weeks later):

- Ask if symptoms compatible with STI
- Physical examination if symptomatic
- STIs diagnosed since last visit (at study site or outside)
- Antibiotic usage
- Question regarding sexual behaviour
- PrEP questionnaire (only at ITM)
- Collection of results of syphilis and HIV testing (performed according to routine practice)

- Sample collection:
 - o Urine sample (first-void) (Ng/Ct NAAT)
 - o Pharyngeal swab (Ng/Ct NAAT)
 - o Anorectal swab (Ng/Ct NAAT)

Visit month 6 (can be between one week early and 6 weeks late):

- Ask if symptoms compatible with STI
- Physical examination if symptomatic
- STIs diagnosed since last visit (at study site or outside)
- Antibiotic usage
- Question regarding sexual behaviour
- PrEP questionnaire (only at ITM)
- Collection of results of syphilis and HIV testing (performed according to routine practice)
- Sample collection:
 - o Urine sample (first-void) (Ng/Ct NAAT)
 - o Pharyngeal swab (Ng/Ct NAAT)
 - o Anorectal swab (Ng/Ct NAAT)

Visit month 9 (can be between one week early and 6 weeks late):

- Ask if symptoms compatible with STI
- Physical examination if symptomatic
- STIs diagnosed since last visit (at study site or outside)
- Antibiotic usage
- Question regarding sexual behaviour
- PrEP questionnaire (only at ITM)
- Collection of results of syphilis and HIV testing (performed according to routine practice)
- Sample collection:
 - o Urine sample (first-void) (Ng/Ct NAAT)
 - o Pharyngeal swab (Ng/Ct NAAT)
 - o Anorectal swab (Ng/Ct NAAT)

Visit month 12 (can be between one week early and 6 weeks late):

- Ask if symptoms compatible with STI
- Physical examination if symptomatic
- STIs diagnosed since last visit (at study site or outside)
- Antibiotic usage
- Collection of results of syphilis and HIV testing (performed according to routine practice)
- Sample collection:
 - o Urine sample (first-void) (Ng/Ct NAAT)
 - o Pharyngeal swab (Ng/Ct NAAT)
 - o Anorectal swab (Ng/Ct NAAT)
- Question regarding sexual behaviour
- PrEP questionnaire (only at ITM)
- Experience of study participation and preference for screening vs. no screening of Ng/Ct (only at ITM)

Unscheduled visits:

- Visits for treatment of detected STIs:

If any asymptomatic (in screening arm) or symptomatic (in both arms) STI is diagnosed via screening (including Ct, Ng, syphilis, HIV or hepatitis C) at any stage during the study, the current practice of contacting the PrEP recipient (typically by telephone) as soon as the test result is known (typically within 7 days) will be followed. The person will be asked to return to the clinic at their earliest convenience for standard management, including contact tracing. If the week-prior testing schema is used then the participant will be typically treated on the day of the clinic visit. These STIs will be treated according to our current guidelines [3]. Participants in the non-screening arm who come for STI testing at unscheduled study visits for example if they have symptoms of an STI, will be informed of the STI diagnosis according to local best practice guidelines.

Persons with an HIV diagnosis will be offered optimal antiretroviral therapy and further best practice management according to our existing PrEP protocol [5]. They will exit this study after the diagnosis of HIV is made.

As is currently the case for all PrEP recipients, participants of this study will be able to attend the PrEP/STI clinic at any point in between the scheduled visits for any health including mental-health related concerns. Participants will be encouraged to attend the clinic for any symptoms compatible with an STI.

Any STIs (Ng, Ct, syphilis, HIV) diagnosed at non-scheduled visits between 0 and 12 months will be included in the primary and secondary outcome. Every effort will be made to obtain laboratory confirmation of these infections and only laboratory confirmed cases will be included in the study outcomes.

Visits as a result of partner notification:

Participants in the non-screening arm will also be tested and eventually treated empirically for Ng/Ct and other STIs if they are alerted for this purpose by partner notification. These visits will be classified as unscheduled visits and they will be tested for Ng/Ct at all three sites. They will also be encouraged to receive empiric therapy for Ng, CT or both according to which STI they were in contact with and what the nature of this contact was in accordance with IUSTI guidelines (<https://www.iusti.org/regions/europe/euroguidelines.htm>).

Visits to assess test-of-cure:

The Belgian National PrEP guidelines do not make a recommendation as to whether or not a test-of-cure is required following treatment for Ng or Ct. In practice most centres reserve performing a test of cure for gonorrhoea infections with a high risk of antimicrobial resistance (such as those from individuals epidemiologically linked to resistant infections) as well as infections with a documented elevated or borderline gonococcal MIC for ceftriaxone. In large part this limitation on performing routine tests of cure is related to patient preference. PrEP patients are followed up 3 monthly which is onerous on patients. They then need to come back for therapy every time they are diagnosed with Ng/Ct. If they need to add an extra test of cure visit to this schedule then many patients regard this as unacceptable or simply not achievable. We will continue with this approach and document all test of cure visits as unscheduled visits. When done, test of cure visits will be performed at the earliest 14 days after the receipt of effective Ng/Ct therapy to rule out

persisting dead DNA causing false positive NAAT test results. Because any positive Ng/Ct test from the test of cure visits is considered a non-resolved old infection, these will not be included in the primary or secondary outcomes as new infections. If however the test of cure was to assess if an Ng infection had cleared and a new Ct infection was detected at the test of cure visit then this would be included as a new infection in the primary and secondary study outcomes.

If a patient has evidence of clinical treatment failure this is a separate issue and we instruct patients to return for further tests if they have persistence of their symptoms. This is also not considered a new infection and will thus not be included in the primary or secondary outcomes as new infections.

All the following investigations are optional for any unscheduled visit:

- Ask if symptoms compatible with STI
- Physical examination
- STIs diagnosed since last visit (at study site or outside)
- Antibiotic usage
- Collection of results of syphilis and HIV testing (performed according to routine practice)
- Sample collection:
 - o Urine sample (first-void) (Ng/Ct NAAT)
 - o Pharyngeal swab (Ng/Ct NAAT)
 - o Anorectal swab (Ng/Ct NAAT)
 - o Pharyngeal or anorectal swab for every site that was Ng NAAT positive (Ng culture)

As is the case for routine PrEP visits currently, at every visit (scheduled or unscheduled) there will be some time for STI counselling and discussions of any concerns of the participants related to the study or not.

Assessing and confirming if a study participant has had a Ct/Ng infection in between study visits.

At the month 3, 6, 9 and 12 visits, the participants will be asked if they have had any symptoms of an STI since their last visit or if they have been tested for an STI since their last visit. If the answer to either of these questions is 'yes', then the study team will proceed with the Ng/Ct diagnosis verification protocol.

1. Obtain further information as to what the symptoms were, if any, and what anatomical sites were tested
2. Find out at which health provider (e.g. general practitioner (GP)) was the diagnosis made
3. Establish what antimicrobial therapy was received
4. Laboratory confirmation will be obtained of test results. The following will be regarded as laboratory proof of a Ct/Ng diagnosis:
 - a. The participant has documented proof of a diagnosis of Ng/Ct based on a laboratory report.
 - b. Laboratory evidence of a positive Ng/Ct diagnosis based on NAAT or Ng culture that can be obtained by the study team via: (1) online laboratory reporting systems

such as COZO, (2) telephonic contact with the laboratory or (3) telephonic contact with the health provider who performed the test.

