4 OBJECTIVES AND ENDPOINTS / OUTCOME MEASURES

Study hypothesis

The study hypothesis is that 3x3 screening in MSM PrEP recipients is not associated with a reduction in the incidence of Ng plus Ct infections over 12 months.

Table 1. PICO Table

Population	All MSM participants aged 18 or older, enrolled to receive HIV PrEP at the Institute of Tropical Medicine, Antwerp (ITM), Hôpital Saint-Pierre (HSP), University Hospital of Gent (UZG), Erasmus Hospital (EH) and Liège University Hospital (CHU) who consented to participate in the trial. Participants must report having had sex with another man in the prior 12 months.
Intervention	Participants in the intervention arm will not be screened for Ng/Ct for a period of 12 months, in reference to the routine practice of screening (and treating screening-positive) participants every 3 months (see 'Comparator'). More specifically, participants in the intervention arm will have 3 site (urethra, pharynx and rectum) sampling performed every 3 months but these testing results will only be reported at the end of the 12 month period. Those testing Ng and/or Ct positive at their last visit in the 12 month period will be recalled and offered treatment even in the case of asymptomatic infection (cfr. current routine care). All individuals with symptomatic infections will be treated according to current best practice guidelines, including contact tracing. Participants in the intervention arm will also be treated if contacted via contact tracing.
Comparator	3x3 screening. For a period of 12 months, all participants will be screened for Ng/Ct at three sites (urethra, pharynx and rectum) every three months according to current Belgian guidelines. If they test positive they will be recalled for treatment for Ng/Ct and contact tracing.
Outcome	
Primary outcome:
 
Incidence rate of Ng plus Ct detected at any site whilst individuals are not screened vs. screened
 
Secondary outcomes:
 
 • Cumulative antimicrobial exposure (ceftriaxone/azithromycin/doxycycline) • Incidence of symptomatic Ng plus Ct • Incidence of syphilis • Incidence of HIV • Cost effectiveness of 3x3 screening vs. no screening • Variations in PrEP users' perceptions towards STI screening (only for ITM subjects)

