5 TRIAL DESIGN

This study is a multi-centre, controlled, randomized trial of 3x3 Ng/Ct screening (comparator) vs. no screening (intervention). It will be performed in the PrEP cohorts situated at the ITM, HSP, CHU, UZG and EH. All men in follow up at these five centres who report having had sex with another man in the previous year and are enrolled for PrEP follow up will be eligible to participate in the study. After signing informed consent participants will be randomized via a computer-generated schema to either 3x3 screening or no Ng/Ct screening (see section 8.3). In both arms, participants will be followed up in an identical fashion including 3x3 screening. The only difference between the arms will be that in the screening arm, Ng/Ct results will be sent by the STI Laboratory to the study physicians and these participants will be treated and partner contact tracing will be done. The STI Laboratory will only process the samples/report the results from the non-screening arm at the end of the study. In both arms, all individuals with symptoms compatible with Ng or Ct will be tested and treated for these infections according to current best practice guidelines. At the end of the 12-month study period, participants whose most recent tests were positive for Ng or Ct will receive treatment for these.

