8.12.2 Withdrawal of consent (discontinuation of trial participation)

In accordance with the Declaration of Helsinki, ICH Good Clinical Practice Guidelines and the Belgian Law on experiments of 2004, a participant has the right to withdraw from the study at any time for any reason without prejudice to his/her future medical care by the physician at the institution. For the purposes of this trial, withdrawal is defined as: The participant would like to withdraw consent from study and is not willing to be followed up for the purposes of the trial at any further visits (i.e. only data collected prior to the withdrawal of consent can be used in the trial analysis).

The details of withdrawal should be clearly documented in the participant's medical records and in the electronic Case Report Form (eCRF).

Handling of Withdrawals

A complete final evaluation should be made at the time of the participant's withdrawal (discontinuation of all study procedures). The End of Study form in the case report form should be completed with an explanation of why the participant is withdrawing.

Participants withdrawn from study will continue to receive standard of care for their condition. This includes, if needed care of any adverse event or complication, whether related or not to the study procedures. The Principal Investigator (PI) will assure this standard of care is provided and he will discuss specific cases when needed with the Coordinating Investigator.

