8.12.3 Loss to follow-up

A participant will be considered lost to follow-up at study closure if he discontinued study visits without informing the study staff and could not be traced. When the investigator has no news of the participant, he/she must make every effort to contact him, to establish the reason for the discontinuation of treatment, and to suggest the participant comes to an end-of-study visit. If all these attempts to contact the participant fail, the investigator can then declare the participant "lost to follow-up". The investigator should document all these attempts in the corresponding medical file.

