2.1. Study design

This study is a multi-centre, controlled, randomized trial of 3x3 Ng/Ct screening (comparator) vs. no screening (intervention). It will be performed in the PrEP cohorts situated at the ITM, HSP, CHU, UZG and EH. All men in follow up at these five centres who report having had sex with another man in the previous year and are enrolled for PrEP follow up will be eligible to participate in the study. After signing informed consent participants will be randomized via a computer-generated schema to either 3x3 screening or no Ng/Ct screening. In both arms, participants will be followed up in an identical fashion including 3x3 screening. The only difference between the arms will be that in the screening arm, Ng/Ct results will be sent by the STI Laboratory to the

study physicians and these participants will be treated and partner contact tracing will be done. The STI Laboratory will only process the samples/report the results from the non-screening arm at the end of the study. In both arms, all individuals with symptoms compatible with Ng or Ct will be tested and treated for these infections according to current best practice guidelines. At the end of the 12-month study period, participants whose most recent tests were positive for Ng or Ct will receive treatment for these.

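### Section 8.7 limits no-screening disclosure to month 0 and month 12, which does not fit the most-recent-test treatment rule for participants whose last sample is month 3, 6 or 9 (minor)

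*Protocol*

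**What the plan says.** Section 8.7 of the protocol withholds the month 3, 6 and 9 results from the no-screening arm and continues: "They will only be informed about the result of the sample taken at month 0 and month 12".

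The treatment commitment is worded differently elsewhere:

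- Protocol section 5: "At the end of the 12-month study period, participants whose most recent tests were positive for Ng or Ct will receive treatment for these". SAP 2.1 repeats the rule.
- Protocol section 4, Table 1: "Those testing Ng and/or Ct positive at their last visit in the 12 month period will be recalled and offered treatment", including when the infection is asymptomatic.
- The trial summary, Table 1 and section 9.3 say the three-monthly results are reported once the 12 months are over, without limiting this to the month 12 sample.

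For early leavers, section 8.12.2 says "A complete final evaluation should be made at the time of the participant's withdrawal" and "Participants withdrawn from study will continue to receive standard of care for their condition". For participants who lose contact, section 8.12.3 asks the investigator "to suggest the participant comes to an end-of-study visit".

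**The concern.** Withholding results during follow-up is the intervention. The end-of-participation treatment rule is the matching safeguard: someone carrying an untreated asymptomatic infection is told and treated when the withholding ends. A participant whose last scheduled sample is month 3, 6 or 9 meets the most-recent-test rule but falls outside the section 8.7 disclosure list. A site reading 8.7 literally would not tell him; a site reading section 5 would treat him. The protocol expects such participants: section 11.1 plans for 10% drop-out and for 5% with only three visits, and HIV diagnosis is an exit.

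What is at stake is the care of a few people with asymptomatic infections, in an arm that departs from the national guideline, and consistency between sites. Symptomatic and partner-notified infections are already tested and disclosed under section 8.7.

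**Working it through.** **1. The rules by last scheduled sample (no-screening arm)**

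| Last scheduled sample | Section 8.7 | Section 5 and SAP 2.1 | Table 1 |
|---|---|---|---|
| Month 12 | Informed | Treat if positive | Recall if positive |
| Month 3, 6 or 9 | Not informed | Treat if positive | Recall if positive, or silent if the last visit means month 12 |

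The mismatch lies in the second row, between section 8.7 and the most-recent-test wording.

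**2. Do the existing routes close the gap?**

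- Section 8.5: repeat testing for a participant who urgently needs to know his status. It is started by the participant, and someone without symptoms may not ask.
- Section 11.3.4: participants who miss a visit are contacted to attend. This covers a missed month 12. A visit outside the window becomes unscheduled under SAP section 3.
- Section 8.7, unscheduled visits: participants who come for STI testing are told the diagnosis. Sampling there is not required: "All the following investigations are optional for any unscheduled visit".
- Section 8.12.2: a final evaluation. Its content is not set, and Table 2 has no column for it.
- Sections 8.12.2 and 9.2: return to standard of care, which under the guideline is three-monthly three-site screening. Retesting is therefore likely. Section 1 notes that some Belgian centres test one site every 3-6 months, without saying whether study sites are among them.
- Section 8.12.3: a suggested end-of-study visit, also without set content.

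Each route makes a test possible. None requires one, and none says what happens to the stored sample. Section 5 has the laboratory handle this arm's samples only when the study ends, so an individual exit triggers nothing.

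**3. Size, from the planning rates in section 11.1**

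- Check on the inputs: mean diagnoses per visit = 0.79×0.15 + 0.18×0.28 + 0.03×0.34 = 0.1791. Over four visits this is 0.716, matching the stated 0.72. Enrolment: 912/0.90 = 1013.3, rounded up to 1014, as stated.
- Probability of at least one diagnosis at a follow-up visit: 0.79×0.14 + 0.18×0.24 + 0.03×0.29 = 0.1625.
- Drop-outs per arm: (1014 − 912)/2 = 51.
- Participants per arm with three visits only: 0.05×456 = 22.8. The documents do not say which visit they miss.

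| Assumption | Participants with a follow-up sample but no month 12 sample | Positive last sample (×0.1625) |
|---|---|---|
| Half the drop-outs gave a follow-up sample; no three-visit participant missed month 12 | 25.5 | 4.1 |
| All drop-outs gave one; no three-visit participant missed month 12 | 51 | 8.3 |
| All drop-outs gave one; every three-visit participant missed month 12 | 73.8 | 12.0 |

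The lower end is not a floor: if only a quarter of drop-outs gave a sample, the first row becomes 12.75×0.1625 = 2.1.

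For scale, with 456 full attenders the design itself leaves 3×456×0.1625 = 222 positive visits at months 3 to 9 undisclosed. Set against that, 4.1 to 12.0 is about 2% to 5%.

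**The case against.** The strongest reply is that section 8.7 was written for completers on a five-visit schedule and simply names their last visit. Table 1 can be read that way, and is then silent on early leavers rather than contradictory. That stands for Table 1. It does not easily extend to section 5 and SAP 2.1: although they apply at the end of the 12 months, the most recent test of someone who missed month 12 is an earlier one.

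A reader might infer that a site cannot satisfy both rules for the same participant. The documents do not support that. A site can retest at exit, disclose that result and treat on it without touching the withheld sample. The retest is then the most recent test.

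A reader might also infer that leavers are abandoned, or wait untreated until month 12. That is not supported either. Section 8.12 provides exit contacts, HIV exits receive best-practice management under section 8.7, and leavers return to routine care. A wait of 3 to 9 months is the worst case, for someone who is never retested.

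Treating on an old sample also has a cost. The background section describes most of these infections as asymptomatic and self-limiting, so some would have cleared. That argues for a retest first, not for leaving the wording as it is.

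The consent pages and the laboratory analytical plan are not available here and may address this. No claim is made about them.

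**Conclusion.** The concern holds in a narrow form. For a no-screening participant whose last scheduled sample is month 3, 6 or 9, the disclosure limit in section 8.7 and the most-recent-test rule in section 5 and SAP 2.1 disagree as written. Existing routes reduce the consequence without guaranteeing a test or release of the stored result.

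The size is roughly 4 to 12 participants with a positive last sample. This assumes that screening-arm rates apply to the no-screening arm, as the sample-size section does, and that between half and all of the drop-outs gave a follow-up sample. Those who are symptomatic, retested or untraceable must still be removed. The documents give no figure for them, so no net number is offered.

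Severity is minor. A reader might look for an effect on the non-inferiority result, but there is none: the stored results are analysed in the same way whether or not the participant is told.

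**What to change.** 1. Amend section 8.7: no-screening participants are informed of the month 0 result and, at the end of their participation, of the result of their most recent scheduled sample.
2. Add to section 8.12: at exit, or when month 12 is declared missed, reachable participants are offered a gonorrhoea/chlamydia retest. If they will not attend, the last stored result is released. Treatment is offered if the result is positive.

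The cost is about one sentence in each place. A few samples are processed earlier than planned. An infection that has already cleared may occasionally be treated, which offering the retest first limits. Section 8.7 counts laboratory-confirmed diagnoses from unscheduled visits up to month 12, so the new text should also say that an exit retest offered under this rule is for care only. Otherwise it could add diagnoses in one arm without a matching visit in the denominator. Withholding during follow-up and the primary analysis stay as they are.
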